# 5. Selection of participants

#### 5.1 Inclusion criteria

- 1. Patients aged 18 years or over.
- 2. Have a diagnosis of MND confirmed by a consultant neurologist
- 3. A clinical diagnosis of respiratory insufficiency according to local protocols, published guidelines and/or specialist opinion.
- 4. Respiratory insufficiency judged by the treating clinician to be severe enough to warrant long-term domiciliary NIV and requiring NIV optimisation within the duration of the study (12 weeks).
  - 5. NIV initiated at home, in an outpatient setting or in hospital if hospital stay is less than or equal to 72 hours post NIV initiation.
- 6. Able to provide informed consent. Adults agreeing to try NIV and able to provide assent (evidence of agreement to take part in the study) but unable to provide informed consent will be able to participate if a consultee (close relative or informal carer) provides a consultee declaration.

#### 5.2 Exclusion criteria

- 1. Already initiated on NIV/CPAP for MND or another reason
- 2. Using tracheostomy ventilation
- 3. No way to connect the ventilation software to the internet whilst in the community
- 4. Patients not requiring optimisation within 12 weeks (e.g. those given the machine but are unable to commence NIV due to lack of social care).

## **5.3 Target Healthcare Professionals**

DENIM will include healthcare professionals already working within the home ventilation service responsible for delivering NIV, typically physiotherapists or nurses. The wider MND team will be invited to shorter training to familiarise themselves with the intervention and trial procedures.

#### 5.4 Participant identification

A member of the patient's care team will identify and consent eligible participants that have been referred to collaborating centres for NIV. We aim to recruit 252 participants during NIV initiation visits. The local research team will be alerted to carry out pre-screening after referral and notify the central team of any written or spoken translation services required.

## **5.5 Informed consent process**

The trial will be coordinated from the Clinical Trials Research Unit (CTRU) in Sheffield Centre for Health and Related Research (SCHARR). A member of the patient's care team at individual sites will identify and consent potential participants. A letter and information sheet about the study (including summary in the appropriate language) will be sent out in advance of their NIV initiation clinic appointment. Where inpatient recruitment is occurring, a letter and information sheet will be given in person and the potential participant given sufficient time to read, ask questions and consider the study. During their clinic appointment they will be rescreened to check eligibility and given the opportunity to ask questions from both the clinical and research team. No study related procedures will occur before the approved consent form is completed, other than initial case note review for eligibility. We will use NHS language interpretation services where required.

Participants can provide written consent. Witnessed consent can be provided for patients unable to speak, read and/or write and can include the use of a communication aid. Participants may choose to nominate a consultee for the duration of their involvement in the trial. For participants unable to consent due to cognitive decline, a consultee declaration may be sought.

For each participant, the original copies of the signed consent forms will be retained by the investigator in the site file but must be made available for inspection by the study monitor. Patients will also receive a copy of the PIS and their consent form to keep, and a copy will be filed in their medical notes and a copy posted or securely emailed [contact] to Sheffield CTRU. Consent (or consultee declaration) will be verbally reconfirmed at each study visit, as recommended by Good Clinical Practice Guidelines. A screening log will be maintained for each site, to document all potential participants screened, whether they were recruited, and any reasons for non-recruitment where this information is available.

Patients who decline to participate will be invited to give consent for the study team to contact them to take part in the ACCESS study, at the point of consent to contact, basic demographic information will be collected.

#### 5.6 Timing of recruitment

Patients initiated in emergency or inpatient settings can be approached and consented within 72 hours of NIV initiation and before discharge. Whilst it is recommended that patients are consented on the day of the NIV initiation, if this is not possible, they can be provided with the telemonitoring equipment and consent, and any baseline data collected remotely. Patients in respiratory failure who

have been provided with NIV equipment but are unable to start using it (e.g. due to lack of social care) could be eligible for recruitment at the time NIV is started at the discretion of the study team.

## 5.7 Co-enrolment guidelines

NIV is part of standard care and there is good evidence that NIV is an effective treatment for people with MND. The trial intervention in DENIM is focused on improving initiation and optimisation of this already proven standard treatment. DENIM will allow co-enrolment in other trials/studies, with permission from the TSC.

## 6. Trial treatment

#### 6.1 Standard care

All sites commence the trial initiating patients in the usual manner. Local variation in site practice is allowed including some sites who have limited telemonitoring services but sites who have an established telemonitoring optimisation service (e.g. more than one preplanned/scheduled telemonitoring review per month) will be excluded. Sites who provide routinely more than two scheduled reviews with access to telemonitoring data within the first two weeks will also be excluded. Sites initiating in hospital but then do not provide more than two scheduled reviews within two weeks will be included.

Initiation location: initiation can occur at home, outpatients or in hospital.

Standard optimisation which is typically, for all patients, a scheduled follow-up telephone review without telemonitoring data at 2 weeks, face to face review at 12 weeks with/without blood gas measurements +/- NIV data downloads + ad hoc consultations triggered by the patient or staff (based on UK wide survey of practice and site consultations [21]).

Overnight oximetry: a limited number of sites use overnight oximetry as a measurement of NIV effectiveness, usually done once the patients used NIV for >4 hours but typically not routinely scheduled for all patients.

As an incentive, participants who are recruited to receive standard care will be signposted to a selection of patient resources (MND Association leaflets, www.mybreathing.mymnd.co.uk, DENIM website).

#### 6-1-1 Site selections

Site inclusion criteria:

 Sites providing initiation AND long-term monitoring AND optimization of NIV for patients with MND according to local and national guidelines. Site exclusion criteria:

- Sites with an established telemonitoring initiation AND optimisation service defined as routinely offering to all patients:
  - o More than one preplanned/scheduled telemonitoring review per month
  - More than two scheduled reviews with access to telemonitoring data within the first two weeks.
  - o Sites initiating in hospital then providing more than two scheduled reviews.

#### **6.2 Intervention**

The trial compares the DENIM implementation strategy, which intends to facilitate a new intensive NIV initiation service to improve NIV delivery, to usual care for NIV initiation and management in MND.

Usual care + a goals-based intensive NIV optimisation package supported by staff training and home telemonitoring.

The DENIM implementation blueprint will outline the aims and justification for the intervention, the scope of the changes proposed and the expected milestones, local/individual adaptations and ways to measure progress/success. The 'Intervention Workbook' will guide staff through each individual stage in the initiation pathway including pre-initiation assessment, initiation visit including consultations to align patient and staff goals (NIV Goals), telemonitoring and patient reviews and ventilation optimisation. Training material will be shaped by consultation with sites and PPI.

#### 6.2.1 Staff education and training

We will train staff to have the knowledge, skills and attitudes required to deliver the intervention using the DENIM implementation blueprint. Staff directly involved with initiating NIV will receive four hours of training plus ongoing peer support and an additional one to two hours of additional training during the process. Other members of the MDT will be offered a one-hour webinar to align their practice with the aims of the project. Staff training aims to be minimally disruptive: it will be all remote, and a mixture of four webinars (which will be recorded to allow replay and flexible learning) supported by self-directed learning + access to online resources adapted from www.niv4mnd.co.uk. Training topics will include evidence-based NIV optimisation strategies and solutions, telemonitoring and oximetry data interpretation and NIV adjustment, the unique challenges of MND (e.g. cognitive impairment, bulbar dysfunction), goal setting and coaching skills, psychological principles [28](e.g. Acceptance and Commitment principles[29]), advanced care planning, staff wellbeing, cultural competencies and health literacy awareness. This will be delivered by our research team with support from other staff

using telemonitoring and telemonitoring companies. It will be sustained through the trial as a network/community of practice and we will offer additional workshops, drop in, peer support and leadership.

#### 6.2.2 Initiation, monitoring and optimisation schedule

The implementation blueprint describes each timepoint where staff will provide additional support. This additional time (one hour at initiation, 30 minutes per timepoint after this) has been accounted for in excess treatment costs.

Staff will meet with the patient as usual at initiation of NIV. They will use the Intervention Workbook which prompts them to complete a structured assessment using simple tools to identify potential barriers to NIV (e.g. bulbar function scale (CNS-BFS[30]), saliva scale[47], cognitive impairment screening tool[31]). The workbook also promotes conversations to promote facilitators to NIV use (e.g. symptoms they wish to treat, advanced care planning) and helps adapt the treatment schedule to the patient's goals.

Once the patient returns home staff will review telemonitoring data and communicate with the patient/carer at 2,5,10 days, 2,3,4, 8, 12 weeks post initiation + adhoc (e.g. following patient contact). Staff can remotely adjust NIV settings (either using the device or by telephone), change masks and communicate + provide support to patients/carers as needed. Patients undergo home overnight oximetry when usage >4hrs/day providing additional objective measures of NIV effectiveness [46].

## 6.2.3 Leadership and change agents

NHS clinician co-applicants and experts in telemonitoring will act as early leaders but the site consultation and training will enable identification of early adopters and change agents who, through the network of ongoing peer support will sustain momentum at sites and with the wider MDT.

#### 6.2.4 Local adaptation and refinement

Our intervention guide will outline the local and individual adaptations allowed during the study. Location adaptation will include limited variation in the patient review schedule and agreed use of telemonitoring and overnight oximetry in usual care. Permitted variation will be based on the current evidence and refined with consultations with sites, experts and local champions and PPI. Ongoing consultations will allow further intervention refinement and support site normalisation of NIV (for example, dissemination of new techniques through local champions).

## 6.2.5 Intervention fidelity and acceptability

We will observe the clinical activity delivered to a patient receiving the intervention. This is planned as part of the pilot following the recruitment of two patients at each site. This will be combined with the research observations (WP2) and results fed back to the research time and (if appropriate) site

team(s) to encourage engagement with the intervention and address any issues. Completeness of the workbooks will be used to understand fidelity to the intervention.

## 6.2.6 Minimising patient and carer burden

The focus of this intervention is on the training and practice change of clinical staff. The main additional activity for patients and carers during this intervention is increased contact with staff to receive the additional support to use NIV. Most/all of this will be by telephone or in a way that meets their needs. If they wish to use it, patients & carers will receive low burden, accessible resources adapted from existing resources already recommended to support NIV initiation (MyBreathing website + paper resources + "MyNIV" initiation paper/digital care plan). Translations and easy read versions will be available (paper + subtitled videos where possible).

#### 6.2.7 Minimising healthcare professional burden

Whilst staff will be expected to review telemonitoring results frequently and adhere to the goal-based approach, patients/carer contact will be driven by clinical need and options for digital communication will be encouraged (e.g TiM/other patient apps where available, phone, video, text or email) to allow staff to successfully incorporate this into their schedule.

## 7. Randomisation and enrolment

Randomisation will occur at the site (NHS Trust) level, with sites randomised to either implement the DENIM strategy or continue with usual care for NIV delivery.

This is a cluster-stepped wedge trial. UK NHS sites will open recruitment for a roll-in period of six months. As sites are opening patients will be recruited to receive the usual care delivered at that site. Following this, every 3 months thereafter, two sites each will receive training and all new patients at that site will receive the intervention until all sites have begun using the intervention.

Sites will be allocated to start the intervention in a random order using constrained random allocation, an analogue of minimisation for trials randomised at the cluster level[32]. Stratification factors will be centre size, telemonitoring use (% of patients currently used) and location of initiation (% of patients initiated as inpatient).

## 8. Outcomes

Secondary patient outcomes can be completed at home in less than 10 minutes using a postal or online questionnaire, or if preferred telephone questionnaire. Baseline data is mostly that collected as part of usual care and will assess the severity, risk of death and risk of NIV ineffectiveness. Additional measures collected at baseline aim to describe the potential factors influencing NIV effectiveness e.g. bulbar dysfunction and home situation. The digital healthcare literacy scale[52] is a three-item scale that can be used to identify those likely to need additional support to use technology.

## 8.1 Primary outcome/endpoint

NIV usage at 12 weeks (the number of days in which patients use NIV for >4hr/day during week 9-12).

## 8.2 Secondary outcomes/endpoints

- NIV usage: NIV usage (first 14 days, first 28 days)
  - o the number of days in which patients use NIV for >4hr/day
- NIV usage: NIV usage (first 14 days, first 28 days, weeks 9-12)
  - o the average (mean) daily usage
  - o the number of patients achieving >4hr/day for > 70% of nights
- Nocturnal respiratory insufficiency using overnight oximetry for a single night at week 12
- Time spent with oxygen saturations <90%
- Oxygen desaturation index (ODI) of 4%
- Patient reported outcome measures: week 12: Quality of life (McGill quality of life questionnaire, developed for patients with a life limiting illness[33]), Dyspnoea-12 (measuring respiratory symptoms, sensitive to change[34], S3NIV (measures respiratory symptoms, sleep quality and NIV-related side effects)[35].
- Health and social care resource use: including EQ5D
- Survival follow-up minimum 12 weeks, maximum of 27 months (week 108)

## 8.3 Exploratory outcomes/ endpoints

These will help explain the mechanisms by which the intervention may deliver positive outcomes and the mechanisms that might predict good/poor outcome which could potentially refine the intervention:

- Ventilator effectiveness (same timepoints as for usage)
  - Tidal volumes
  - Ventilator asynchronies
  - Apnoea hypopnoea index
  - o Leak
- Nocturnal evidence of REM related desaturation
  - o evidence of REM related desaturation trace).
- Explanatory implementation outcomes
  - Assessment of changes in barriers and facilitators to implementation at sites, pre and post intervention
  - o Fidelity: Percentage completeness of the first consultant workbook
  - Fidelity: Number of times remote monitoring was reviewed at the pre-specific times
  - Fidelity: Number of times workbook was reviewed per participant
  - Fidelity: Number of actions taken

## 8.4 Internal pilot feasibility study

The initial 12 months of recruitment (study month 20) will run as an internal pilot. Sheffield CTRU will aggregate study data to assess the feasibility of the research and intervention protocols based on feasibility outcomes (Table 1). Two checkpoints will be used: the first for site initiation (at study month 14, month six of recruitment period) and the second for recruitment, intervention delivery and data collection when the first four sites have been switched onto delivering the intervention (at study month 20, which is month 12 of recruitment period equating to halfway through recruitment).

Table 1. Pilot feasibility study criteria

Table 1. Pilot Criteria	Red (% met)	Amber (% met)	Green (% met)
Phase 1. Site Initiation			
Site set up (number of centres recruited first patient)	<7 centres (<60%)	7-11 (60- 99%)	12 (100%)
Phase 2: Recruitment and follow up			
2. Participant Recruitment (number of centres achieving their individual target recruitment rate)		7-11 (60- 99%)	12 (100%)

**DENIM:** Delivering Effective Non-Invasive ventilation in Motor neuron disease using intensive remote support

3. NIV adherence (primary outcome) obtained from patients who have completed the study	<70%	70-99%	100%
4. Patients received a clinical review within the specified time windows (week 4, intervention fidelity).	<75%	75-99%	100%

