Internal pilot/feasibility criteria	Pilot green criteria:  1. Site set up  Number of centres recruited first patient: 12  (100%) at study month 14, month six of recruitment period)  2. Participant Recruitment: number of centres achieving their individual target recruitment rate (100%) at study month 20, which is month 12 of recruitment period equating to halfway through recruitment  3. Data collection: NIV adherence (primary outcome) obtained from patients who have completed the study 100% at study month 20, which is month 12 of recruitment period equating to halfway through recruitment  4. Intervention delivery: Patients received a clinical review within the specified time windows

	(week 4, intervention fidelity). 100% at study month 20, which is month 12 of recruitment period equating to halfway through recruitment
Setting	Outpatient or inpatient NIV initiation
Participants	Adults with a diagnosis of MND confirmed by a consultant neurologist and a clinical diagnosis of respiratory insufficiency according to local protocols, published guidelines and/or specialist opinion. And have respiratory insufficiency judged by the treating clinician to be severe enough to warrant long-term domiciliary NIV and requiring NIV optimisation within the duration of the study (12 weeks).
Intervention & control groups	Intervention: A theory-based package of staff education, highly intensive support, monitoring and optimisation using telemonitoring during the first 12 weeks of NIV use  Control: standard care
Primary outcome(s)	NIV usage at 12 weeks (the number of days in which patients use NIV for >4hr/day during week 9-12)
Secondary/exploratory outcome(s)	NIV effectiveness: NIV usage (w4), ventilation effectiveness (w4&12) (e.g. tidal volumes, ventilator asynchronies, apnoea hypopnoea index, leak)  Patient reported outcome measures (w12):  Quality of life (McGill quality of life questionnaire, developed for patients with a life limiting illness),  Dyspnoea-12 (measuring respiratory symptoms, sensitive to change), S3NIV (measures respiratory symptoms, sleep quality and NIV-related side effects)  Health and social care costs  EQ5D

**DENIM:** Delivering Effective Non-Invasive ventilation in Motor neuron disease using intensive remote support

	Survival follow-up minimum 12 weeks, maximum of 27 months
Duration of recruitment period and first enrolment date	1 st May 2025, 96 weeks

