Duration of follow-up	12 weeks follow up. All participants survival followed up at week 108
Target sample size	252 (12 clusters)
Definition of end of trial	All participants completed 12 weeks of NIV optimisation and all participants survival collected at week 108.

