## 11. Statistics

#### 11.1 Sample size

The primary outcome is the number of days in which patients use NIV for >4hr, assuming standard deviation of ten0 days with a high skew. A modest change in survival and quality of life requires a large change in adherence; we assume a mean difference of six days to reflect this. Assuming a

conservative estimate where each site recruits, on average one patient per month in months 7-24 and three patients in the six months roll in period this will recruit a total of 252 patients. Allowing for 15% drop-out, 214 participants provide 90% power to detect an increase of six days in adherence assuming an inter-cluster coefficient of 0.05 and a two-sided 5% significance level. The sample size was calculated using a modified version of the Stata stepped wedge macro which allowed non-integer number recruited per step.

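### Pilot criterion 3 is scored among an undefined group of study completers, so no Table 1 criterion tests the 15% drop-out assumption; separately, 7 of 12 centres is amber by count but red by percentage

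*Protocol*

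**What the plan says.** Section 8.4 of the protocol makes the first 12 months of recruitment an internal pilot with two checkpoints: site set-up at recruitment month 6 (study month 14), and recruitment, data collection and intervention delivery at recruitment month 12 (study month 20). Table 1 gives red, amber and green bands for four criteria.

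- **Criterion 3** is "NIV adherence (primary outcome) obtained from patients who have completed the study", with red below 70%, amber 70-99% and green 100%. The Trial Summary files it under data collection and repeats the denominator: "NIV adherence (primary outcome) obtained from patients who have completed the study 100% at study month 20".
- **Criterion 1** (centres that have recruited a first patient) has a red cell that reads "<7 centres (<60"%). Amber is 7-11 centres, labelled 60-99%, and green is 12 centres.
- **Criterion 2** (centres meeting their recruitment rate) carries the same amber label. Its red cell is not legible in the text available for this review.
- **Criterion 4** is a week-4 clinical review within its time window.

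Section 11.1 sizes the trial on retention: "Allowing for 15% drop-out, 214 participants provide 90% power to detect an increase of six days in adherence". The target is "252 (12 clusters").

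**The concern.** The sample size depends on the share of all recruits who provide a primary outcome. Criterion 3 is the only Table 1 row about the primary outcome, and its denominator is completers. If completers are those who did not discontinue, each death, full withdrawal or loss before weeks 9-12 leaves numerator and denominator together, and the score does not move. The pilot could then read green while the evaluable number falls below 214.

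For the centre criteria, each band is given both as a count and as a percentage. If the two labels disagree at the red/amber boundary, the table gives two answers for the same result.

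**Working it through.** **The plan's own arithmetic.** Section 11.1 plans "one patient per month in months 7-24 and three patients in the six months roll in period" at each site.
- Recruits: 12 × (3 + 18) = 252.
- Evaluable: 252 × (1 − 0.15) = 214.2, so 214. Both figures reproduce, and the retention the design needs is 85%.

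**Participants due at the second checkpoint (recruitment month 12).**
- Recruited: 12 × (3 + 6) = 108.
- Past week 12, counting three months back (recruited by month 9): 12 × (3 + 3) = 72.
- Past week 12, counting exactly 12 weeks back (month 9.24): 36 + 3.24 × 12 ≈ 75.

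**Reading A: completers are those who did not die, withdraw fully or become lost.** Take 72 due and let every completer have ventilator data.

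| Loss before weeks 9-12 | Completers | Criterion 3 | Share of those due with outcome |
|---|---|---|---|
| 15% (planned) | 61 | 100%, green | 85% |
| 30% (illustrative) | 50 | 100%, green | 69% |
| 40% (illustrative) | 43 | 100%, green | 60% |

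The score is the same in every row. The 30% and 40% losses are illustrations; the documents give no such rates.

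**Reading B: completers are everyone whose week-12 date has passed.** The score on plan is 85%. Green at 100% needs no loss at all among 72-75 people, although the design allows for about 11 (0.15 × 72 = 10.8; 0.15 × 75 = 11.3). A trial exactly on plan is amber.

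**What a shortfall costs.** I used a standard stepped-wedge variance (Hussey-Hughes) with 12 sites, six steps of two, seven periods, categorical time, SD 10, ICC 0.05, a six-day difference and a two-sided 5% level.
- 214 evaluable (85%): power 84.8%.
- 176 (70%): 78.5%.
- 151 (60%): 72.9%.

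This model does not reproduce the stated 90% at 214. The protocol used a modified Stata macro that is not shown, so I rely only on the fall between rows.

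**Where a green line could sit on an all-due denominator.** The standard error at 85% is √(0.85 × 0.15 / n) = 0.042 for n = 72 and 0.041 for n = 75. The binomial figures below ignore clustering by site.
- Green at 85% or more with true retention of 85%: P(at least 62 of 72) = 0.48; P(at least 64 of 75) = 0.55. A trial on plan would miss green about half the time.
- Green at 80% or more: P(at least 58 of 72) = 0.89; P(at least 60 of 75) = 0.91. If true retention were 70%, the same counts would be reached with probability 0.03 to 0.04.
- A one-sided 5% allowance puts the line at 0.85 − 1.645 × 0.042 ≈ 0.78.

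**Centre bands, out of 12.**

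| Centres | % | By count | By percentage |
|---|---|---|---|
| 6 | 50.0 | red | red |
| 7 | 58.3 | amber | red |
| 8 | 66.7 | amber | amber |
| 11 | 91.7 | amber | amber |
| 12 | 100 | green | green |

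Seven is the only value that conflicts.

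**The case against.** The strongest reply is that criterion 3 is a data-capture check, as its label in the Trial Summary says. Asking whether ventilator data arrive for people who finish is a fair feasibility question, and 100% is a coherent green level for it. Some restriction is also needed at month 12, because many recruits will not yet have reached week 12, and the phrase may have been meant only in that sense. This stands as far as it goes: the term is undefined, and Reading A is the natural reading rather than a stated rule. Its main support is that section 9.3 records withdrawals on a form that sets completion against discontinuation.

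A reader might infer that every withdrawal escapes the criterion. The protocol does not support that. Under section 9.3, people who leave the intervention or stop NIV can stay in data collection, and the intermediate withdrawal option may still yield ventilator data. Section 9 has adherence reach the trials unit by telemonitoring in both arms, and section 9.4 counts a participant as lost only if no data can be obtained at study close. The gap is confined to death, full withdrawal and loss.

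A reader might also infer that attrition goes unwatched. It does not: the DMEC reviews progress every six months and can recommend stopping for futility, and the TSC can close the trial (sections 13.1 and 13.2). Neither section attaches a threshold to attrition.

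On the centre bands, the criteria are worded as numbers of centres, so the count is the likely operative rule and the percentage a rounded gloss. Section 8.4 attaches no action to any colour. That keeps the point minor.

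**Conclusion.** The point holds in a limited form. Criterion 3 needs its denominator defined, because neither reading serves: one cannot register death, full withdrawal or loss, and the other makes green unattainable for a trial on plan. On the natural reading no Table 1 criterion tests the 85% retention behind 214 of 252. How much this matters depends on actual attrition, which the documents do not forecast beyond the 15% allowance. If retention were 70%, 176 would be evaluable, and power on the model above would be about six points below its value at 214. The figure of 72-75 due assumes recruitment runs to plan.

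The count and percentage conflict at 7 of 12 is certain for criterion 1. For criterion 2 only the amber label can be seen to mismatch, so a clash between two of its bands should not be claimed. The conflict is minor. The denominator is worth correcting before the second checkpoint.

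**What to change.** **Criterion 3 (Table 1 and Trial Summary).**
- Define the denominator as all consented participants whose week-12 date has passed, and report deaths before week 12 separately so that they are not read as data-collection failures.
- Keep the existing 70% red line.
- Re-base green on the planned 85% with an allowance for sampling error at 72-75 due. A line near 78-80% is one workable choice. Exactly 85% is not the only correct value, and a trial on plan would miss it about half the time.
- If data capture among completers is still wanted, keep it as a separate figure and define completer.

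**Criteria 1 and 2.** Use the counts alone (red below 7, amber 7-11, green 12), or change 60% to 58%.

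The cost is an edit to Table 1 and the matching summary lines, with whatever amendment approval that needs. The data are already collected, and the sample size and analysis are unchanged.
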